9.3. Treatment Compliance

Once a subject has been treated with additional therapy, the subject should be exited from the study per the Schedule of Assessments ([Section 20.1 - Appendix A](#)).

9.4. Randomization and Blinding

While there will be no randomization in this non-interventional extension study, the masking from the Parent study will be protected in this trial until the Parent study has completed and is appropriately unmasked.

10. STUDY DRUG MATERIALS AND MANAGEMENT

Not Applicable

11. ASSESSMENT OF EFFICACY

11.1. Best Corrected Visual Acuity (BCVA)

Best Corrected Visual Acuity (BCVA) will be measured using ETDRS electronic visual acuity (eVA) and will be collected at every visit. BCVA will be recorded as total letter score in each eye following refraction. Visual acuity testing should precede any examination requiring contact with the eye.

In order to provide standardization and well-controlled assessments of BCVA during the study, all BCVA assessments must be performed by trained staff who are certified on the study procedure using certified VA equipment/lanes.

If eVA cannot be performed for any reason, BCVA will be measured using a standard ETDRS chart. If Roman letters are not familiar to the subject, Tumbling E charts may be used.

11.2. Central Subfield Thickness as Measured by SD-OCT

Retinal thickness and disease characterization will be assessed at every visit via spectral domain optical coherence tomography (SD-OCT) (Heidelberg SPECTRALIS® or Zeiss Cirrus™). The SD-OCT instrument and technician must be certified prior to enrolling any subjects. The technician is encouraged to use the same certified photography equipment throughout the subject's study participation. All photos should be taken by the same photographer, whenever possible, on each subject per research site. Images will be sent to a central reading facility for analysis and interpretation in a masked fashion.

12. ASSESSMENT OF SAFETY

12.1. Safety Parameters

12.1.1. Intraocular Pressure

Intraocular pressure (IOP) will be measured by applanation tonometry (Tonopen or Goldmann) at every visit and results will be recorded in mmHg. A single measurement will be made at approximately the same time of day. The technician is encouraged to use the same tonometry method throughout the subject's study participation. Tonometers must be calibrated for accuracy before the first subject screening at that site and according to the manufacturer specifications during the study, until the last subject has exited the study at that site.

12.1.2. Slit-Lamp Biomicroscopy

Slit-lamp biomicroscopy, including magnification, will be performed at every visit and consistent with standard clinical practice. This procedure should be conducted in the same manner for all subjects and will include an assessment of each of the following as normal or abnormal: eyelids, cornea, anterior chamber, iris and lens. All abnormal findings will be described.

12.1.2.1. Cataract Lens Grading

If an abnormal finding of cataract is noted for the lens during the slit-lamp exam, the cataract should be assessed for nuclear opalescence, cortical opacity and posterior subcapsular opacity. Graders must verify training on the grading procedure provided in the Manual of Procedures.

12.1.2.2. Anterior Chamber Cells

Anterior chamber cells will be assessed clinically using a field size of 1 mm slit beam and using a standardized grading scale ranging from 0 to 4+, as defined in Table 1 ([SUN 2005](#)).

Table 1: Anterior Chamber Cell Grading Scale

| Score | Cells in Field |
|-------|----------------|
| 0 | <1 |
| 0.5+ | 1-5 |
| 1+ | 6-15 |
| 2+ | 16-25 |
| 3+ | 26-50 |
| 4+ | >50 |

12.1.2.3. Anterior Chamber Flare

Anterior chamber flare will be assessed clinically via slit lamp using a standardized scale ranging from 0 to 4, as defined in Table 2 ([SUN 2005](#)).

Table 2: Anterior Chamber Flare Grading Scale

| Score | Description |
|-------|--|
| 0 | None |
| 1+ | Faint |
| 2+ | Moderate (iris and lens details clear) |
| 3+ | Marked (iris and lens details hazy) |
| 4+ | Intense (fibrin or plastic aqueous) |

12.1.3. Dilated Ophthalmoscopy

A dilated fundus examination at every visit will include an assessment of each of the following as normal or abnormal: vitreous, retina, macula, choroid and optic nerve. All abnormal findings will be described.

12.1.3.1. Vitreous Haze

Vitreous haze will be assessed clinically via indirect ophthalmoscopy using a standardized photographic scale ranging from 0 to 4, as defined in Table 3 ([Nussenblatt 1985 as modified in Lowder 2011](#)).

Table 3: Scale for Determining Degree of Vitreous Haze

| Score | Description |
|-------|--|
| 0 | no inflammation |
| +0.5 | trace inflammation (slight blurring of the optic disc margins and/or loss of the nerve fiber layer reflex) |
| +1 | mild blurring of the retinal vessels and optic nerve |
| +1.5 | optic nerve head and posterior retina view obscuration greater than +1 but less than +2 |
| +2 | moderate blurring of the optic nerve head |
| +3 | marked blurring of the optic nerve head |
| +4 | optic nerve head not visible |

12.2. Adverse and Serious Adverse Events

12.2.1. Definition of Adverse Events

12.2.1.1. Adverse Event (AE)

An **Adverse Event** (AE) is any untoward medical occurrence associated with the use of a drug in humans and does not have to have a causal relationship with study treatment.

An AE can therefore be any unfavorable and unintended sign (that could include a clinically significant abnormal laboratory finding), symptom, or disease temporally associated with the use of a medicinal product, whether or not considered related to the medicinal product.

Whenever possible, the Investigator should group signs or symptoms that constitute a single diagnosis under a single AE term (eg, “cough, rhinitis and sneezing” might be grouped together as “upper respiratory tract infection”).

An AE may include:

- Any sign, medical diagnosis or symptom
- Any new undesirable medical occurrence or unfavorable or unintended change of a pre-existing condition that occurs during or after test article administration.

NOTE:

- o The disease under study (ie, non-infectious uveitis) or sign or symptom associated with the disease are not considered adverse events, unless more severe than expected for the subject's condition
- o Symptoms associated with disease, which are consistent with the subject's usual clinical course are not considered adverse events, unless the subject experiences worsening of symptoms more severe than expected or unless the symptom(s) meet the criteria for an SAE
- Clinically significant (as determined by the Investigator) laboratory abnormalities, ophthalmic assessments or vital signs (eg, requiring discontinuation of test article, specific treatment or a change in subject management). If possible, abnormal laboratory results or changes in vital signs that meet the definition of an AE should be reported as a clinical diagnosis rather than the abnormal laboratory value (eg, “hypertension” rather than “blood pressure increased”)

12.2.1.2. Serious Adverse Event (SAE)

A serious adverse event is an AE occurring during any study phase (ie, baseline, treatment, washout, or follow-up), and at any dose of the investigational product, comparator or placebo, that fulfils one or more of the following:

- Death

- Life-threatening (ie, if in the view of the Investigator or Sponsor, the event’s occurrence places the subject at immediate risk of death); it does not include an AE that, had it occurred in a more severe form, might have caused death
- In-patient hospitalization or prolongation of existing hospitalization
 - “In-patient” hospitalization means the subject has been formally admitted to a hospital for medical reasons. This may or may not be overnight. It does not include presentation at a casualty or emergency room.
- A persistent or significant incapacity or substantial disruption of the ability to conduct normal life functions
- A congenital anomaly in the offspring of a subject who received study drug
- Important medical events that may not result in death, be life-threatening or require hospitalization may be considered an SAE when, based upon appropriate medical judgment, they may jeopardize the subject and may require medical or surgical intervention to prevent one of the outcomes listed in this definition

12.3. Relationship to Study Drug

Causality is the relationship of an AE to study drug and will be assessed by the investigator as follows in Table 5:

Table 5: Causality Definitions

| Causality | Definition |
|------------------|--|
| Related | There is a reasonable causal association with administration of the study drug; the event is confirmed by stopping and/or restarting the drug or is not explained by any other reasonable hypothesis |
| Not related | There is no causal or temporal relationship to the study drug; related to other etiologies such as concomitant medications or conditions |

12.4. Recording Adverse Events

Adverse events spontaneously reported by the patient/subject and/or in response to an open question from the study personnel or revealed by observation will be recorded during the study at the investigational site. The AE term should be reported in standard medical terminology when possible. For each AE, the investigator will evaluate and report the onset (date and time), resolution (date and time), intensity, causality, action taken, serious outcome (if applicable), and whether or not it caused the patient to discontinue the study.

The **intensity** of each AE will be graded using National Cancer Institute (NCI) Common Terminology Criteria for Adverse Events (CTCAE) v 4.03. The criteria can be accessed at: http://evs.nci.nih.gov/ftp1/CTCAE/CTCAE_4.03_2010-06-14_QuickReference_5x7.pdf.

The term “severe” is a measure of intensity. A severe AE is not necessarily a serious AE.

Grade refers to the severity of the AE. The CTCAE displays Grades 1 through 5 with unique clinical descriptions of severity for each AE based on this general guideline:

| | |
|---------|---|
| Grade 1 | Mild; asymptomatic or mild symptoms; clinical or diagnostic observations only; intervention not indicated |
| Grade 2 | Moderate; minimal, local or noninvasive intervention indicated; limiting age-appropriate instrumental activities of daily living (ADL) |
| Grade 3 | Severe or medically significant but not immediately life-threatening; hospitalization or prolongation of the hospitalization indicated; disabling; limiting self-care ADL |
| Grade 4 | Life threatening consequences; urgent intervention indicated |
| Grade 5 | Death related to AE |

12.5. Reporting Serious Adverse Events

Prompt reporting of a SAE requires:

- Completion and transmission of SAE information to the Sponsor within 24 hours of the investigator’s knowledge of the event. The SAE information should be completed as thoroughly as possible before transmittal to the Sponsor. **It is very important that the investigator provide his/her assessment of causality to study treatment at the time of initial reporting of the SAE.**
- Prompt reporting of additional information for previously reported SAEs should follow the same reporting timeframe as initial reports.

If an ongoing SAE changes in intensity or the relationship to study drug, a follow-up SAE report should be sent to the Sponsor within 24 hours after the clinical site becomes aware of the change in status.

12.5.1. Transmission of SAE Reports

An adverse event that is serious must be reported on an SAE form to the Sponsor immediately, but no later than 24 hours after the investigator becomes aware of the event.

SAE reporting information should be transmitted to the Sponsor via email or fax as provided below.

Chiltern, Inc.
[contact]
Toll free fax US: [contact]
Toll free fax India: [name]

Please refer to the study reference binder for complete contact information. Contact the Medical Monitor with any questions regarding a potential SAE.

If an ongoing SAE changes in intensity or the relationship to study drug, a follow-up SAE report should be sent to the Sponsor within 24 hours after the clinical site becomes aware of the change in status.

12.5.2. Regulatory Reporting Requirements for SAEs

The Sponsor will determine which SAEs qualify for expedited reporting. Reports of those SAEs that qualify for expedited reporting will be unmasked for the individual subject and submitted to regulatory agencies in accordance with applicable local regulation. Expedited reports will also be distributed to Investigators without revealing the treatment assignment and will be submitted to IRB/IEC in accordance with institutional guidelines and local regulation.

13. STATISTICS

A detailed statistical analysis plan will be prepared for this study. The plan will contain a discussion of the statistical methods, a description of the computational algorithms and data handling conventions, and specifications for the data summaries and listings. It will be finalized before database lock.

13.1. Randomization

There will be approximately 30 subjects enrolled from the Parent study, CLS1001-301, where there were two masked arms (4.0 mg CLS-TA and sham). No additional randomization is planned for this study.

13.2. Determination of Sample Size and Level of Significance

The sample size of approximately 30 subjects at approximately 40 centers was based on clinical considerations appropriate for a non-interventional extension study.

13.3. Subject Disposition, Demographic and Baseline Characteristics

Subject disposition, demographic, and baseline characteristics (sourced from the Parent study) will be summarized descriptively by treatment group and overall.

13.4. Analysis Population

13.4.1. Safety Population

Safety population will include all enrolled subjects who successfully complete the crossover visit (Day 0). The Safety Population will be used for safety analyses.

13.4.2. Intent-to-Treat Population

Intent-to-treat (ITT) population includes all enrolled subjects. ITT population will be used for efficacy analyses.

13.5. Analysis Methods

13.5.1. Primary Efficacy Endpoint

Time to rescue therapy (dosing with a drug when efficacy of the Parent study investigational products is no longer adequate)

13.5.2. Primary Efficacy Analysis

All data collected in the study database will be presented in the listings. Listings will include change from baseline. Baseline is the Crossover Visit.

Time to Rescue Therapy will be analyzed using Kaplan-Meier analysis including 95% confidence intervals, log rank p-value for difference between treatments, and quartiles.

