2. SYNOPSIS

| | |
|--|--|
| Name of Sponsor/Company: Clearside Biomedical, Inc. | |
| Name of Investigational Product: Triamcinolone Acetonide (CLS-TA) Injectable Suspension | |
| Name of Active Ingredient: Triamcinolone Acetonide | |
| Title of Study: MAGNOLIA: Multi-Center, Non-Interventional Extension Study of the Safety and Efficacy of CLS-TA for the Treatment of Macular Edema associated with Non-Infectious Uveitis | |
| Study center(s): Multi-Center | |
| Principal Investigator: Multi-Center | |
| Studied period: 6 Month Duration Estimated date first patient enrolled: October 2016 Estimated date last patient completed: September 2017 | Phase of development: Non-interventional study |
| Objectives: Primary: Demonstrate the maintenance of efficacy of CLS-TA, up to 6 months following exit from Parent study, as shown by the need for additional therapy or the increase in maintenance therapy, for the symptoms of uveitis. Secondary: Determine the maintenance of safety of CLS-TA up to 6 months following exit from Parent study, as demonstrated by incidence of adverse events related to Parent study investigational product | |
| Number of patients (planned): approximately 30 | |
| Diagnosis and main criteria for inclusion: Participation in CLS1001-301, non-infectious uveitis Phase 3 (Parent) study without additional therapy for uveitis | |
| Investigational product, dosage and mode of administration: No investigational product administered in this study | |
| Reference therapy, dosage and mode of administration: None | |
| Criteria for evaluation: Efficacy: Mean time to additional uveitis therapy or change in maintenance therapy for uveitis Safety: Incidence of Adverse Events and serious adverse events grouped by organ system, relatedness to Parent study investigational product, and severity | |
| Statistical methods: All data collected in the study database will be presented in the listings. Listings will include change from baseline. Baseline is the Crossover Visit. Time to Rescue Therapy will be analyzed using Kaplan-Meier analysis including 95% confidence intervals, log rank p-value for difference between treatments, and quartiles. | |

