6.1. Primary Objective

Demonstrate the maintenance of efficacy of CLS-TA, up to 6 months following exit from Parent study, as shown by the need for additional therapy or the increase in maintenance therapy, for the symptoms of uveitis.

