7.2. Number of Subjects

The study population will include approximately 30 adult subjects that successfully complete the Parent study without requiring additional therapy to treat symptoms for uveitis as defined by the protocol. The expected duration of participation in the study is up to 24 weeks from study entry. The complete inclusion and exclusion criteria are presented below in Section 8.

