8. SELECTION AND WITHDRAWAL OF SUBJECTS

8.1. Subject Inclusion Criteria

Subjects are eligible for participation in this study if s/he meets all of the following criteria:

1. Enrolled in the Parent study, CLS1001-301, through Visit 8/Month 6
2. Willing and able to provide written informed consent prior to any study procedures; willing to comply with the instructions and attend all scheduled study visits

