8.2. Subject Exclusion Criteria

1. Received additional therapy for the treatment of uveitis or prohibited medication as defined in Section 6.2 of the Parent protocol, CLS1001-301
2. Require additional therapy for the treatment of uveitis or prohibited medication as defined in Section 6.2 of the Parent protocol, CLS1001-301 at the time of the Crossover visit

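### The log-rank p-value planned for the primary endpoint compares Parent arms among entrants selected after Parent randomisation, and the supplied text does not say that this randomisation no longer protects it

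*Combined protocol and SAP*

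**What the plan says.** Section 13.5.2 analyses time to rescue therapy by "Kaplan-Meier analysis including 95% confidence intervals, log rank p-value for difference between treatments, and quartiles". The synopsis repeats the test: "log rank p-value for difference between treatments, and quartiles". Section 7.3 says no product is given in the extension, and Section 13.1 names two Parent arms, 4.0 mg CLS-TA and sham. The difference between treatments can therefore only mean CLS-TA against sham as assigned in the Parent study.

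Entry is decided after that assignment:

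- Section 7.2 describes "approximately 30 adult subjects that successfully complete the Parent study without requiring additional therapy to treat symptoms for uveitis".
- Section 8.1 requires fresh written consent and that the subject was "Enrolled in the Parent study, CLS1001-301, through Visit 8/Month 6".
- Section 8.2 excludes anyone who "Received additional therapy for the treatment of uveitis or prohibited medication as defined in Section 6.2 of the Parent protocol, CLS1001-301", and anyone who needs such treatment at the Crossover visit.

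Section 13.4.2 takes everyone enrolled in the extension as the efficacy set and names it intent-to-treat. Section 9.4 states that "there will be no randomization in this non-interventional extension study", and Section 13.1 says the same. Section 6.1 gives the aim: "Demonstrate the maintenance of efficacy of CLS-TA, up to 6 months following exit from Parent study". Section 13 promises a detailed statistical analysis plan and says of it: "It will be finalized before database lock". That plan is not among the documents.

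**The concern.** A log-rank test between randomised arms is normally read as a comparison of like with like. Here the groups are what remains of each arm after a filter that the Parent treatment could itself have influenced. The filter (no additional uveitis therapy by Month 6) is closely related to the endpoint (rescue therapy afterwards).

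Suppose rescue differed between arms in the Parent study and subjects differ in their underlying risk of relapse. The two groups then enter the extension with different average risk, even if no treatment effect remains. The p-value mixes that difference with any continuing effect of CLS-TA.

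This is the only p-value planned for the primary endpoint, and the objective is worded as a demonstration. A reader who takes the test as protected by randomisation could credit or blame CLS-TA for a difference that partly reflects who was allowed to enter. Describing how long subjects unrescued in the Parent study stay unrescued remains legitimate. The problem is the between-arm test without a caveat.

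**Working it through.** **Text check.** The sections that bear on the p-value are 6.1, 9.4, 13, 13.1, 13.2, 13.4.2, 13.5.1, 13.5.2, 13.5.8 and the synopsis. None calls it exploratory, nominal or descriptive, and none says that Parent randomisation does not protect it. Section 13.2 gives no significance level, power or effect size, so there is no planned figure to reproduce.

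**Inputs from the documents.** About 30 entrants; visits every 6 weeks; 24 weeks of follow-up (Sections 7.1 and 7.2).

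**Assumed inputs.** The documents give no Parent rescue rates, allocation ratio or spread of relapse risk. Assumed here are the proportion unrescued in each Parent arm (S), the allocation ratio, and gamma-distributed frailty with mean 1 and variance t.

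**Model.**

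- Parent study: S = (1 + tL)^(−1/t), so the cumulative hazard is L = (S^(−t) − 1)/t. At t = 0, L = −ln S.
- Mean frailty among unrescued subjects is 1/(1 + tL) = S^t.
- With no residual effect, the CLS-TA to sham hazard ratio at crossover is (S_CLS/S_sham)^t.
- Example, 70% against 50% unrescued, t = 1: L_CLS = 1/0.70 − 1 = 0.43 and L_sham = 1/0.50 − 1 = 1.00. Mean frailty is 0.70 and 0.50, so the ratio is 0.70/0.50 = 1.40.
- Reversed, 50% against 70%: 0.50/0.70 = 0.71. The lean is now towards CLS-TA.

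**Simulation.** Events were rounded up to 6-weekly visits and censored at 24 weeks, with a two-sided 5% log-rank test. The post-crossover hazard was the sham Parent hazard times the residual ratio. The entrant split follows from allocation and S; for example, with 1:1 and 65%/55%, 30 × 65/120 = 16.25, giving 16/14. Except for the 90%/80% row, each setting had 20,000 trials (standard error at most 0.3 percentage points).

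False finding that CLS-TA is worse, no residual effect, nominal 2.5%, 1:1 Parent allocation:

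| Unrescued CLS-TA/sham | Entrants | Crossover hazard ratio, t = 0.5, 1, 2 | False worse, t = 0.5, 1, 2 |
|---|---|---|---|
| 60%/60% | 15/15 | 1.00, 1.00, 1.00 | 2.6, 2.4, 2.5% |
| 90%/80% | 16/14 | 1.06, 1.13, 1.27 | 2.9 to 3.8% |
| 65%/55% | 16/14 | 1.09, 1.18, 1.40 | 3.1, 4.0, 5.0% |
| 70%/50% | 17/13 | 1.18, 1.40, 1.96 | 3.9, 6.2, 10.0% |
| 80%/40% | 20/10 | 1.41, 2.00, 4.00 | 6.4, 12.8, 25.6% |

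With no heterogeneity (t = 0) the rate is 2.0 to 2.4% in the 60%/60%, 65%/55%, 70%/50% and 80%/40% settings.

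With 3:2 allocation and t = 2, the last three rows become about 4%, 7.5% and 18%. The splits are 19/11, 20/10 and 23/7. The last is rounded from 22.5/7.5, and 22/8 would give a somewhat higher figure.

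**Power for a residual hazard ratio of 0.5.** With comparable entrants (both arms given the sham survivors' frailty) and 1:1 allocation, power runs from 8.1% (15/15, t = 2) to 26.0% (20/10, t = 0) over the 60%/60%, 65%/55%, 70%/50% and 80%/40% settings. For scale, 80% power at 1:1 needs 4 × (1.96 + 0.84)² / (ln 0.5)² ≈ 66 events, and 30 subjects cannot give more than 30.

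Adding selection at t = 1 changes the chance of missing the effect (100% minus power) as follows:

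- 65%/55%: 100 − 12.3 = 87.7% becomes 100 − 9.0 = 91.0%.
- 70%/50%: 100 − 13.5 = 86.5% becomes 100 − 6.8 = 93.2%.
- 80%/40%: 100 − 15.7 = 84.3% becomes 100 − 3.3 = 96.7%.

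**The case against.** The strongest reply is that nobody is misled. The study is openly non-interventional, Sections 9.4 and 13.1 say there is no randomisation, and Sections 5.2 and 7.2 say who enters. Section 13.2 sets no significance level or power, and no decision rests on the p-value. Section 13.4.2 states exactly who is in its set, so the intent-to-treat label is largely a matter of naming. Section 13.5.8 speaks of the primary analysis in general and does not mention the log-rank test. The detailed analysis plan may yet add a caveat.

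Most of this stands, and it limits the point. The documents do not show that the sponsor means the test as confirmatory, and the absence of a caveat can be asserted only for the supplied text. It does not remove the point: as written, the primary analysis yields a between-arm p-value with nothing to tell the reader what it lacks, and the label on the set suggests a protection it does not have.

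A reader might go further and infer that the test is biased against CLS-TA. The documents do not support that. Bias through rescue selection needs both unequal Parent rescue and heterogeneous risk. It leans against CLS-TA only if CLS-TA reduced Parent rescue, and towards CLS-TA if it increased it. It is absent if Parent rescue was equal or risk is homogeneous. Completion and re-consent could push either way. Nor do the documents show that the exclusion in Section 8.2 and the endpoint in Section 13.5.1 share one definition; they are only closely related.

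**Conclusion.** The point holds for the protocol text. The planned log-rank comparison is made in a set selected after Parent randomisation on a criterion tied to the endpoint, so it lacks that randomisation's protection, and the supplied text does not say so.

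The size is unknown. Over the assumed settings in which CLS-TA reduced Parent rescue, the distortion ranges from negligible to large, and nothing in the documents makes the large figures more plausible than the small ones. All figures rest on the gamma-frailty model and the assumed rescue rates and allocation.

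It is also tempting to say that a null result would be produced by selection. The arithmetic does not support that. With about 30 entrants a null result is likely either way; outside the extreme setting selection adds to that but is the smaller part. This is a defect of interpretation in the primary analysis that should be fixed, and wording is enough to repair it.

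**What to change.** - **Section 13.5.2 and synopsis.** Keep the Kaplan-Meier estimates by Parent arm, with 95% confidence intervals and quartiles, as descriptive. Drop the log-rank p-value, or add: *The log-rank p-value is exploratory; entrants were selected after Parent randomisation, so it is not protected by that randomisation.*
- **Section 13.4.2.** Rename the set *Extension enrolled population*.
- **Section 13.3.** Add to the summary by treatment group the numbers randomised, eligible and enrolled per Parent arm, and the Week 24 (Crossover) characteristics.
- **Detailed analysis plan.** Carry the same wording there.

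The cost is small. No new data are collected from subjects: Appendix A makes the Crossover visit the Parent Week 24 visit, so those values exist. Numbers randomised and eligible per arm come from the Parent study once it is unmasked. What is lost is a formal p-value, or its standing, with low power under the assumptions above.
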